9.6.5.9 Human leukocyte antigen (HLA)-genotyping

In order to identify the MHC alleles in subjects with AESI and/or SAEs related to vaccine, an additional 2 mL of blood sample will be collected for HLA genotyping.

9.6.6 Immunogenicity Assessments

9.6.6.1 Detection of ELISA Antibodies against S1-RBD of SARS-CoV-2

Anti-S1-RBD antibody titers will be measured by ELISA kit. A serial dilution is to begin at 1:20, followed by 1:100, 1:1000, 1:10,000 and 1:100,000 for test sera. The levels of anti-S1-RBD antibody are expressed as linear titers of an end point dilution for each tested sample. SoftMax Titer Calculation Program (Molecular Devices Co.) is used to calculate the titers. For seroconversion detected by UBI SARS-CoV2 S1-RBD ELISA, it is defined as a 4-fold increase in antibody titer from baseline. If the titer is <20, a value 2-fold lower will be imputed (1:10). If the titer is >100,000, a titer 2-fold higher (1:200,000) will be imputed for the purpose of calculating the geometric mean and geometric mean fold increase. The practice will be applied on the specimens of all subjects.

9.6.6.2 Detection of Antibody Titers Which Inhibit S1-RBD:ACE2 binding

Antibody titers for ability to inhibit S1-RBD:ACE2 binding will be measured by ELISA kit. The dilution fold is at 1:10 for test sera. Antibody levels which inhibit S1-RBD:ACE2 binding are expressed in $\mu\text{g/mL}$ as titers for a test sample based on a standard curve. SoftMax Titer Calculation Program (Molecular Devices Co.) is used to calculate the titers. Specimens that do not react in the test are considered with < 1.6 $\mu\text{g/mL}$ titer in this SARS-CoV-2 qNeu Ab ELISA. For samples with a titer <1.6 $\mu\text{g/mL}$, a value 2-fold lower (i.e. 0.8 $\mu\text{g/mL}$) will be imputed for the purpose of calculating the GMT and GMFI. Similarly a titer with >25 $\mu\text{g/mL}$ will be imputed 2-fold higher for calculation of the means.

9.6.6.3 Neutralizing Antibody Titers against SARS-CoV-2

Neutralizing antibody titers will be measured by CPE-based live virus neutralization assay using Vero-E6 cells challenged with SARS-CoV-2 (SARS-CoV-2-TCDC#4). The study will be conducted in P3 lab at Academia Sinica, Taipei. Determination of SARS-CoV-2 virus specific neutralization titer is to measure the neutralizing antibody titer against SARS-CoV-2 virus based on the principle of NT₅₀ titer ($\geq 50\%$ reduction of virus-induced cytopathic effects). Virus neutralization titer of a serum is defined as the reciprocal of the highest serum dilution at which 50% reduction in cytopathic effects are observed and results are calculated by the method of Reed and Muench. In seroconversion rate detected by live virus neutralization test, it is defined as a 4-fold change in antibody titer from baseline.

9.6.6.4 Detection of T Cell Response

Human peripheral blood mononuclear cells will be used in the detection of T cell response. Antigen-specific interferon-gamma (IFN- γ) measurement to assess cellular (T cell) immune response will be measured by ELISpot method. Intracellular cytokine staining and flow cytometry will be used to evaluate CD4⁺ and CD8⁺ T cell responses.

9.6.7 Overall Study Stopping Rules

Study administration with UB-612 vaccine will be halted and the DSMB will convene to determine if the study should be terminated for any safety concerns. See [Section 9.7](#) for DSMB details. Overall study stopping rules is listed below.

- One or more \geq grade 4 adverse reaction or serious adverse event possibly associated with vaccination
- Occurrence of grade 3 adverse events associated with vaccination in 3 or more of subjects in a treatment group participants or more (including injection-site reaction, systemic reaction, and change of the safety laboratory measures)
- Required by sponsor
- Required by regulatory authority
- Required by institutional review board (IRB).
- The sponsor may also end the study for administrative reasons.

Should the study be terminated prematurely, the sponsor will provide written notification to all investigators and regulatory authorities specifying the reason(s) for early termination. The investigator must inform the institutional review board (IRB)/independent ethics committees (IEC) promptly and provide the reason(s) for the termination. Previously dosed subjects will be assessed through all planned study safety visits.

9.6.8 Appropriateness of Measurements

The immunogenicity and safety assessments planned for this study are generally recognized as reliable, accurate, and relevant to the diagnostic modality and underlying disease/condition.

9.7 Data and Safety Monitoring Board (DSMB)

To enhance the safety and integrity of the study data, a DSMB will evaluate clinical and laboratory safety data of the first 6 subjects (the Sentinel Groups) in each group to evaluate the risk of remaining 14 subjects, and a total of 20 subjects in each group before advancing to the next higher dose level/cohort. The DSMB will consist of an independent medical monitor, a statistician, and 1 or more experts in vaccinology who have experience serving on DSMBs. The DSMB members will review safety data and to provide a recommendation on dosage escalation, or early termination in case there is a concern regarding safety. Both the DSMB and the Sponsor must approve further immunization in case there is no concern of safety.

9.8 Surveillance and Laboratory Diagnosis of SARS-CoV-2 Infection during Clinical Trial

During the observation period of the clinical trial, the participants with fever, cough and other respiratory symptoms should immediately go to the designated hospital. The doctor or investigator will collect the nasopharyngeal/throat swabs and to perform CT and other imaging examinations to analyse whether it is caused by SARS- CoV-2 infection. In the event of SARS-CoV-2's infection during the clinical trial, it is necessary to conduct a case investigation, and the critically ill or dead cases need to continue to conduct a special investigation, mainly to analyze whether there is an ADE or VAERD phenomenon.

In addition to SARS-CoV-2 nucleic acid detection, multiple pathogens will be detected for differential diagnosis of swabs.

10 STATISTICAL METHODS

The statistical planning and analysis of the trial will be performed by the designated contract research organization.

10.1 Statistical and Analytical Plans

A statistical analysis plan will be prepared and finalized prior to database lock of the study. The statistical analysis plan will include full details of all planned statistical analyses.

10.2 Datasets or Populations Analysed

Safety Set

The Safety Set (SS) will consist of all subjects receiving at least one injection of the UB-612 vaccine. The Safety Set is for safety evaluation in analysis.

Full Analysis Set

The Full Analysis Set (FAS) will consist of subjects who receive two vaccinations, have at least one immunogenicity assessment after vaccination, and without SARS-CoV-2 infection between Day 0 and Day 56. Subject receive prohibited medication/treatment/vaccine during pre-specified period has impact on immunogenicity may exclude from the FAS set. The FAS set is the primary analysis set for immunogenicity evaluation.

Modified Intention-to-Treat Set

The modified intention-to-treat Set (mITT) will consist of subjects who receive at least one vaccination and have at least one immunogenicity assessment after the first or second vaccination. The mITT is also analysed for immunogenicity evaluation.

Per Protocol Set

The Per Protocol Set (PPS) will be a subset of FAS. PPS includes subjects who receive two vaccinations, have at least one immunogenicity assessment on Day 42 or 56 after vaccination, and without SARS-CoV-2 infection between Day 0 and Day 56. Subjects who had major protocol deviations as determined by the Study Team or who received prohibited medication/treatment/vaccine during the pre-specified period **leading to an impact on immunogenicity will be excluded from the PPS set**. The PPS is also analysed for immunogenicity evaluation as a sensitivity analysis.

10.3 Demographic and Other Baseline Characteristics

Demographic and baseline characteristic data will be summarized for each vaccine group and overall. Descriptive statistics (N, mean, standard deviation, median, minimum, and maximum) will be presented for continuous variables. The number and percentage of subjects in each category will be presented for categorical variables. No formal testing of demographic or baseline characteristics will be performed.

10.4 Safety Evaluation

All safety assessments, including AEs, PEs, VS, ECG and clinical laboratory evaluations, where indicated, will be presented using descriptive statistics for each vaccine group of UB-612. Data will be summarized for each vaccine group and overall.

Solicited Adverse Event

Solicited AEs recorded on e-diary will be summarized by the severity grading scales by vaccine groups. Numbers and percentages of subjects experiencing each adverse event will be presented for each symptom severity by study groups. Summary tables showing the occurrence of any local or systemic adverse event overall and at each time point will also be presented.

Adverse Event

This analysis applies to all adverse events occurring during the study, recorded in AE eCRF, with a start date on or after the date of vaccination. AEs occurring during the study will be coded using the most recent version of Medical Dictionary for Regulatory Activities (MedDRA). The adverse events will then be grouped by MedDRA preferred terms into frequency tables according to system organ class.

All reported adverse events, as well as adverse events judged by the investigator as at least possibly related to study vaccine, will be summarized according to system organ class and preferred term within system organ class. When an adverse event occurs more than once for a subject, the maximal severity and strongest relationship to the vaccine group will be counted.

Separate summaries will be produced for the following categories, such as serious adverse events and AEs related to UB-612 vaccine will be presented. Data listings of all adverse events will be provided by subject.

Physical Examination

All physical examination findings will be listed and summarized by time point and study vaccine group. Shift table will be also presented, if appropriate.

Vital Signs

All vital sign findings will be listed and summarized by time point and study vaccine group.

ECG

ECG findings will be listed and summarized by time point and study vaccine group. Shift table will be also presented, if appropriate.

Laboratory Evaluations

Laboratory safety data will be analysed descriptively by time point and study vaccine group. Shift table for laboratory data will be shown by visit using categorization of laboratory according to local laboratory's normal reference range.

10.4.1 Analysis of Primary Safety Endpoint

- Occurrence of adverse reactions within 7 days after vaccination
All adverse reactions within 7 days after vaccination will be summarized with frequencies and percentages by study vaccine group and each vaccination.
- The percentage of subjects with \geq Grade 3 adverse events within 7 days after vaccination
The subject who has \geq Grade 3 solicited AE or \geq Grade 3 unsolicited AE within 7 days after vaccination will be counted. The number and percentage of counted subjects will be demonstrated by study vaccine group and each vaccination.

10.4.2 Analysis of Secondary Safety Endpoint

- Occurrence of adverse events (AE) till Day 56
AEs till Day 56 will be presented with number and percentage by system organ class, preferred term, and study vaccine groups.
- Occurrence of serious adverse events (SAE) till Day 56
The number and percentage of SAEs within 56 days will be displayed in summary table by study vaccine groups.
- Occurrence of serious adverse events during the whole follow-up period (6 months)
The number and percentage of SAEs during the whole follow-up period (6 months) will be presented in summary table by study vaccine groups.
- Occurrence of adverse events of special interest during the study period
Adverse events of special interest during the study period will be summarized with number and percentage from the mapping result by MedDRA. Details will be defined in the statistical analysis plan.
- Changes of safety laboratory measures
Changes of safety laboratory measures will be summarized with descriptive statistics by study vaccine group and time point. ANCOVA model with laboratory baseline values as covariate will analyse changes of safety laboratory measures for testing the difference among study vaccine groups. Pair-wise comparisons of least square means from the ANCOVA model will be presented. Intra-group difference in safety laboratory measures will also be analysed by paired t test.

10.5 Immunogenicity Evaluation

10.5.1 Analysis of Immunogenicity Endpoints

- Geometric mean titer (GMT) of antigen-specific antibody (Anti-S1-RBD) on Day 14, 28, 42, 56, 112, and 196.
GMT of antigen-specific antibody of antigen-specific antibody (Anti-S1-RBD) on Day 14, 28, 42, 56, 112, and 196 will be described by descriptive statistics and the 95% confidence interval for study vaccine group. Additionally, the difference among vaccine groups will be analyzed by ANCOVA model under log-transform data with baseline level as covariate, if appropriate. Pair-wise comparisons of least square means from the ANCOVA model will be presented. The reverse cumulative distribution plot will be provided to display the distribution of the GMT of Anti-S1-RBD by time points for each vaccine group.
- Seroconversion rate (SCR) of antigen-specific antibody (Anti-S1-RBD) on Day 14, 28, 42, 56, 112, and 196.
The SCR will be presented as count and percentage in frequency table, and the 95% exact (Clopper-Pearson) confidence interval will be provided as well. The group comparison among dose groups will be assessed by Fisher's exact test.
- Geometric mean fold increase of antigen-specific antibody (Anti-S1-RBD) on Day 14, 28, 42, 56, 112, and 196.
The geometric mean fold increase (GMI) in each study vaccine group is summarized by descriptive statistics and the 95% confidence interval for study vaccine group. The difference among vaccine groups will be analysed by ANOVA. Pair-wise comparisons of least square means from the ANOVA model will be presented. The reverse cumulative distribution plot will be provided to display the distribution of the GMI of Anti-S1-RBD by time points for each vaccine group.

10.5.2 Analysis of Exploratory Immunogenicity Endpoints

- GMT of neutralizing antibody against SARS-CoV-2 on Day 14, 28, 42, 56, 112 and 196
GMT of neutralizing antibody against SARS-CoV-2 on Day 14, 28, 42, 56, 112 and 196 will be summarized by descriptive statistics and the 95% confidence interval for study vaccine group. Additionally, the difference among vaccine groups will be analysed by ANCOVA model under log-transform data with baseline level as covariate, if appropriate. Pair-wise comparisons of least square means from the ANCOVA model will be presented. The reverse cumulative distribution plot will be provided to display the distribution of the GMT of neutralizing antibody against SARS-CoV-2 by time points for each vaccine group.
- SCR of neutralizing antibody against SARS-CoV-2 on Day 14, 28, 42, 56, 112 and 196
SCR of neutralizing antibody against SARS-CoV-2 on Day 14, 28, 42, 56, 112 and 196 will be presented as count and percentage in frequency table, and the 95% exact (Clopper-Pearson) confidence interval will be provided as well. The group comparison among dose groups will be assessed by Fisher's exact test.
- Geometric mean fold increase of neutralizing antibody against SARS-CoV-2 on Day 14, 28, 42, 56, 112 and 196

Geometric mean fold increase of neutralizing antibody against SARS-CoV-2 on Day 14, 28, 42, 56, 112, and 196 will be summarized by descriptive statistics and the 95% confidence interval for study vaccine group. The difference among vaccine groups will be analysed by ANOVA. Pair-wise comparisons of least square means from the ANOVA model will be presented. The reverse cumulative distribution plot will be provided to display the distribution of the GMI of neutralizing antibody against SARS-CoV-2 by time points for each vaccine group.

- Distribution of titers

For ELISA, ACE2:RBD inhibition ELISA, and Neutralizing antibody titers, reverse cumulative distribution of titers will be displayed at Day 14, 28, 42, 56, 112 and 196.

- Correlation between the immune response detected by ELISA and live virus neutralization test

Pearson correlation coefficient will be used to measure the dependence of the immune response detected by anti-S1-RBD ELISA and live virus neutralization test, and the dependence of the immune response detected by qNeuAb ELISA (for research use only) and live virus neutralization test. Correlation coefficient between ELISA (anti-S1-RBD ELISA or qNeuAb ELISA) and live virus neutralization test will be presented by each matched time points and overall. In addition, the consistency of the immune response detected by ELISA (anti-S1-RBD ELISA or qNeuAb ELISA) and live virus neutralization test will be analysed by linear regression with the result of ELISA (anti-S1-RBD ELISA or qNeuAb ELISA) as dependent variable and the value of live virus neutralization test as independent variable. The scatter plot with the linear relationship and its 95% confidence interval and 95% prediction interval will be drawn.

- Positive rate and level of antigen-specific interferon-gamma (IFN- γ) measured by ELISpot on Day 7, 28, 35, and 196.

Positive rate and level of antigen-specific interferon-gamma (IFN- γ) in each visit and each group is summarized by descriptive statistics and the 95% confidence interval for study vaccine group. Fisher exact test will be used to compare the positive rate among vaccine groups. The difference among vaccine groups in level of antigen-specific IFN- γ will be analysed by ANOVA.

- CD4⁺ and CD8⁺ T cell responses using intracellular cytokine staining and flow cytometry on Day 7, 28, 35, and 196.

The specific memory CD4⁺ T cells and memory CD8⁺ T cell responses of each group and each time point will be counted, and the percentage of cells in which at least one of the three indexes is positive. The level of cell response will be expressed by the percentage of positive cells, and summarized by descriptive statistics. Count the positive rate of cell reaction in each group, expressed by the number and percentage, and calculate the 95% confidence interval of the positive rate.

ANOVA will be used to compare the reaction level among vaccine groups and Fisher exact test will be used to compare the positive rate among vaccine groups.

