In all groups, an informed consent and the eligibility of subjects will be checked at screening period. The 1st study vaccine administration will be done immediately after blood draw at Visit 2 to evaluate baseline laboratory safety and humoral / cellular immune response. The first 6 subjects in each group will be closely monitored by the study staff at least 2-4 hours after vaccination, and subsequent 14 subjects in each group will be monitored at least 60 minutes after vaccination (for vital signs change and adverse events). The post-vaccination diary card for 7-day solicited adverse events after vaccination will be given to subjects with a suitable instruction. The first 6 subjects in each group will visit clinics at Day 3 (Visit 3) and Day 7 (Visit 4) for monitoring safety, and 14 subsequent subjects could be enrolled if no \geq grade 3 AE or SAE related to vaccine is reported.

At Visit 4 (Day 7), subjects will return for laboratory safety check and have blood drawn for cellular immune response and hand in the diary card.

At Visit 5 (Day 14), the subjects will return to clinics and have blood drawn for humoral immune response.

At Visit 6 (Day 28), the 2nd study vaccine administration will be done after blood draw for

humoral / cellular immune response, and subject will be closely monitored for 60 minutes after vaccination. The post-vaccination diary card will be dispensed to subject.

At Visit 7 (Day 35), subjects will return for laboratory safety check, have blood drawn for cellular immune response, and hand in the diary card.

At Visit 8 (Day 42), the subjects will return to clinics and have blood drawn for humoral immune response.

At Visit 9 (Day 56), the subject will return to clinics and have blood drawn for humoral immune response.

At Visit 10 (Day 112) and Visit 11 (Day 196), the blood draws will be performed to observe the persistence of immunogenicity.

All adverse events and serious adverse events will be monitored from Day 0 until Day 196.

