8.2 Visit 2 (Day 0) –Baseline: 1st Vaccination

- (1) Check inclusion and exclusion criteria
- (2) Assign subject number
- (3) Record any pre-vaccination medical event as medical history since last visit.
- (4) Conduct physical examination.
- (5) Measure vital signs.
- (6) Perform a urine pregnancy test
- (7) Collect blood sample for immunogenicity tests (central laboratory) before vaccination
 - Humoral immune response
 - Cellular immune response
- (8) Perform 1st vaccination. Observe closely during vaccination and at least 2-4 hours after vaccination for the first 6 subjects in each group and at least 60 minutes after vaccination for subsequent 14 subjects at site (for the change of vital sign or adverse event).
- (9) Perform 12 lead ECG within 1 hour after vaccination.
- (10) Dispense self-evaluation diary card. Instruct the subject to monitor body temperature and complete the diary correctly.

Subject will be instructed to record any solicited adverse events occurring during a 7-day post-vaccination period on the diary card. If the subject perceives any signs or symptoms are progressing or serious, contact the investigator or their delegates immediately. Additional return visits can be scheduled by the investigators when necessary.

(11) Review concomitant medications.

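### V-122 compares T-cell levels between dose groups by unadjusted ANOVA and gives the scheduled Day 0 cellular value no stated use; adjusting for it would gain precision if it correlates with the post-dose level above about 0.13

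*Supplement*

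**What the plan says.** Section 10.5.2 of the V-122 protocol specifies two T-cell comparisons among the dose groups. For ELISpot: "The difference among vaccine groups in level of antigen-specific IFN- γ will be analysed by ANOVA". For CD4+ and CD8+ responses by intracellular cytokine staining (ICS): "ANOVA will be used to compare the reaction level among vaccine groups". Neither sentence names a covariate or a transformation.

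The listed analysis days leave out Day 0. The ELISpot endpoint reads "Positive rate and level of antigen-specific interferon-gamma (IFN- γ) measured by ELISpot on Day 7, 28, 35, and 196", and the ICS endpoint uses the same four days.

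A Day 0 cellular value is nevertheless planned for everyone. Section 7.1 says: "The 1st study vaccine administration will be done immediately after blood draw at Visit 2 to evaluate baseline laboratory safety and humoral / cellular immune response". In section 8.2, the Visit 2 list includes "Collect blood sample for immunogenicity tests (central laboratory) before vaccination", with humoral and cellular response as its two items. The blood table in section 7.2 allots 35 of the 40 mL drawn on Day 0 to the cellular assays.

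Elsewhere the same plan does adjust for baseline. For neutralizing titres, section 10.5.2 says "the difference among vaccine groups will be analysed by ANCOVA model under log-transform data with baseline level as covariate, if appropriate"; section 10.5.1 does the same for anti-S1-RBD titres, and section 10.4.2 for the safety laboratory values.

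**The concern.** Baseline adjustment is written in for the antibody titres and left out for the T-cell levels. For antibody it turned out to have nothing to work on: section 5.5 of the V-123 protocol (Table 5-1) reports Day 0 geometric mean titres of 10.00 and 2.50 with no confidence interval in any V-122 group, so the covariate is constant. The T-cell readouts are the immunogenicity measures for which a varying Day 0 value remains possible. Entry is screened by IgG, RT-PCR and exposure history (sections 7.4.2 and 7.4.3), and none of these measures T-cell reactivity.

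Two things could be lost. The first is precision, because variation between subjects that is already present on Day 0 stays in the residual. The second is comparability. The synopsis states that doses are allocated sequentially, so any difference in Day 0 level between cohorts, whether by chance or by enrolment period, carries into the unadjusted dose contrast in proportion to the correlation.

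**Working it through.** There is no plan figure to reproduce. Section 10.8 states that no sample size or power computation was done, and no T-cell standard deviation, Day 0 value or correlation appears in the documents.

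**Inputs.** From the documents: n = 20 per group (section 10.8) and k = 3 groups, so N = 60. Assumed: correlation rho between the Day 0 and post-dose level, from 0 to 0.7; two-sided alpha of 0.05; a linear relation with common slope; and baselines that differ between groups only by chance.

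**Formula.** For a pairwise contrast, ANOVA has N − k = 57 error degrees of freedom and ANCOVA has 56. The expected variance ratio, ANCOVA to ANOVA, is

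(1 − rho²) × [1 + 1/(N − k − 2)] = (1 − rho²) × (1 + 1/55) = (1 − rho²) × 1.018.

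The second factor is the price of estimating the slope. The standard-error ratio is the square root, and the equivalent sample size is the reciprocal of the variance ratio.

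**Break-even.** (1 − rho²) × 1.018 = 1 gives rho = √(1/56) = 0.134.

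**Results.** The last column is ANCOVA power at the difference for which ANOVA has 80% power, 0.90 SD.

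| rho | variance ratio | change in SE | equivalent sample size | power |
|---|---|---|---|---|
| 0 | 1.018 | +0.9% | 0.98 times | 79.3% |
| 0.3 | 0.91 × 1.018 = 0.927 | −3.7% | 1.08 times | 82.9% |
| 0.5 | 0.75 × 1.018 = 0.764 | −12.6% | 1.31 times | 89.3% |
| 0.7 | 0.51 × 1.018 = 0.519 | −28% | 1.93 times | 97.3% |

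A simulation with 4,000 runs per value gave variance ratios of 1.02, 0.92, 0.76 and 0.51, in agreement with the formula.

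**Imbalance.** Under the linear relation, a Day 0 gap of d SD between two cohorts shifts the unadjusted contrast by rho × d SD. By chance alone, the gap between two groups of 20 has a standard deviation of √(2/20) = 0.32 SD, so at rho = 0.5 the typical shift is 0.5 × 0.32 = 0.16 SD. That chance part is already counted in the table. A systematic gap between sequential cohorts would come on top of it, as bias in the unadjusted contrast.

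**The case against.** The strongest reply is that the gain may be nil. Subjects are screened as unexposed, and both antibody readouts were undetectable in all of them before vaccination. If Day 0 T-cell values also sit at background, the covariate does nothing, just as for antibody. This stands. The V-122 reference list does include a T-cell study whose title covers unexposed people, so the question was open, but no figure can be taken from that.

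A reader might therefore infer too much: that ANOVA is wrong here, that it certainly wastes precision, or that adjustment is free. The documents support none of these. ANOVA is a valid test, the correlation is not reported, and adjustment costs one degree of freedom and, at rho = 0, about 1.8% of variance on average. The shortcut √(1 − rho²), which gives reductions of 5%, 13% and 29%, leaves out that cost and slightly overstates the gain.

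Two practical objections also stand. The ICS level is a percentage of positive cells and can be zero, while section 9.6.6 gives substitution values only for the two ELISAs; a log analysis therefore needs its own zero rule. And because section 10.7 rules out imputation, ANCOVA drops any subject without a Day 0 result, whom ANOVA would keep.

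Little depends on the comparison. The endpoints are exploratory, section 5.2 ties dose choice to seroconversion, and the V-123 and V-205 protocols summarise T-cell data descriptively. Section 10.1 leaves full detail to an analysis plan that is not shown. That weakens the point without removing it, because the protocol positively names the test.

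**Conclusion.** The point holds as a low-impact improvement. V-122 schedules a Day 0 cellular sample for every subject, names ANOVA without a covariate for both T-cell levels, and gives the Day 0 value no role in the comparison. ANCOVA is the better default because the stakes are uneven: a standard error larger by about 0.9% if Day 0 carries no information, against one smaller by 3.7% to 28% if the correlation lies between 0.3 and 0.7, with break-even near 0.13. It would also adjust for Day 0 differences between cohorts that were not randomised, though not for other differences between them.

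The facts about the plan are certain. The size of the gain rests wholly on the assumed correlation, on a roughly linear relation on the analysis scale, and on nearly complete Day 0 data.

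**What to change.** In V-122 section 10.5.2, replace ANOVA for the ELISpot and ICS levels by ANCOVA on log-transformed levels, with dose group as factor and the Day 0 value as covariate, at Days 7, 28, 35 and 196. Add three statements:

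- how zero values are handled before taking logs, on Day 0 and afterwards;
- that ANOVA is the fallback where Day 0 shows no variation or is missing, with the criterion fixed before post-dose results are examined;
- that Day 0 levels are summarised by dose group, with the number of subjects lacking a Day 0 result.

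The cost is wording, one degree of freedom, and the possible loss of subjects without a Day 0 result from the adjusted model. No extra blood, visit or subject is needed.
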